## EXECUTIVE SUMMARY

This clinical trial is a feasibility study to assess the performance of an Artificial Pancreas (AP) device using the Artificial Pancreas System (APS©) platform for subjects with type 1 diabetes using rapid acting insulin as well as pre-prandial inhaled insulin (Technosphere® Insulin Inhalation System by MannKind Corporation). This is a follow-up study to the approved feasibility study IDE G110093. The new proposed study and IDE G110093 use the same device and follow the same clinical protocol with the addition of the pre-prandial inhaled insulin in this new proposed feasibility study. The CGM for this proposed study is the next generation of Dexcom CGMs, the G4® System which was recently approved by the FDA. The goal of this proposed study is to explore the feasibility of using multiple insulin delivery routes in order to mimic the physiology of both 1st and 2nd phase insulin secretion. The intent is to exploit the rapid action achieved by inhaled insulin to compensate for part of the meals and utilize the conventional subcutaneous route for management of basal insulin and as second phase meal-related insulin. Preliminary analysis of the results of IDE G110093 have been very encouraging and are supportive of this new proposed study using inhaled insulin to reduce the post-prandial peak. The AP device is a closed-loop between a Dexcom® G4® System (Dexcom® Incorporated, San Diego, CA) continuous glucose monitor (CGM) and a OneTouch® Ping® Glucose Monitoring System (Animas Corp, Westchester, PA) subcutaneous insulin delivery pump (CSII). The AP device is controlled by a zone-Model Predictive Control (zone-MPC) algorithm augmented by a safety algorithm named the Health Monitoring System (HMS). The clinical study will include 12 to 20 adults subjects aged 21 to 65 years old.

The study consists of an evaluation of the Artificial Pancreas device during a 24-hour closed-loop in a clinic environment (Sansum Diabetes Research Institute, Santa Barbara, CA). The 24-hour period includes:

- 2 unannounced meals (evening dinner and breakfast of 50 g CHO each) preceded with a nominal dose of Technosphere® inhaled insulin;
- 1 period of 30 minutes of exercise at 50% of the predicted heart rate reserve (HRR) preceded with a snack and followed by a snack 3 hours later (on Day 2);
- complete night from 12:00 am to 7:00 am;

The subject will arrive at approximately 4:00 pm to the CRC (clinical research center), the closed-loop will be initiated at approximately 4:30 pm that same day and continued until 4:30 pm the next day. A physician will be monitoring the patient with the artificial Pancreas (AP) device at all time.

The proposed study will evaluate the performance of the AP device combined with Technosphere® Insulin Inhalation Powder in predicting the fall and rise of glucose values and in regulating insulin delivery to mitigate extreme blood glucose variations during the following challenges:

- following unannounced meals,
- during a nocturnal period, and
- during a period of active exercise.

The goal is to demonstrate that the AP device is able to maintain the subject blood glucose within a safe range at all times. One of the objectives of the study will be to measure the percent of time spent in the following zones:

- [80-140] mg/dL at all times unless described otherwise
- [80-140] mg/dL during the nocturnal period
- [70-180] mg/dL postprandial, for 5 hours following the unannounced meals
- [70-150] mg/dL during and for 3 hours following exercise

In particular, an analysis will report on 1-hour and 2-hour postprandial glucose level and 6-hour area-under-the-curve (AUC) when compared to G110093 to evaluate the impact of the Technosphere® insulin (only for those subjects who enrolled in both clinical studies).

It is anticipated that following the planned challenges, glucose value might increase temporarily beyond those ranges. These excursions will be reviewed and analyzed (value and duration) and the study will determine how the AP device mitigates those excursions and maintains glucose levels within a safe and acceptable range. The clinical study will also review any event that occurs during the course of the 24-hour closed-loop: hypoglycemic events, hyperglycemic events, outside intervention, other Adverse Event, Serious Adverse Events, Unanticipated Adverse Device Effect, and device complaints for the commercial devices used. A root cause analysis of the event will be performed to determine if it is related to the device or the drug and if the drug, which drug (subcutaneous or Technosphere® Insulin). Safety of the patient will remain the primary goal. The goal of the AP device combined with the Technosphere® Insulin Inhalation Powder (with Gen2C inhaler) is to operate without outside intervention even when challenged by meals or exercise unless the outside intervention is requested by the Health Monitoring System (HMS). The subject will just inhale one 10U dose prior to meals. This is approximately 4U of subcutaneous insulin.

The table below is a synopsis of the proposed clinical protocol.

Title of the protocol	Feasibility Study using Zone-MPC Controller (Zone-Model Predictive Control) and Health Monitoring System (HMS) and Technosphere® Insulin Inhalation System from MannKind Corp.
Sponsor	Sansum Diabetes Research Institute (SDRI)
Investigational Device	Artificial Pancreas (AP) device: Artificial Pancreas System platform (APS©) from the University of California, Santa Barbara and SDRI with: 
 
• OneTouch® Ping® Glucose Management System with modified Meter-Remote from Animas® Corp or the OmniPod® Insulin Management System from Insulet Corp.
 
• Dexcom® G4® CGM System (CGM) from Dexcom® Corp
 
• Control algorithm: zone-Model Predictive Control (zone-MPC) with safety Health Monitoring System (HMS)
 

Drug	Approved rapid acting insulin (subcutaneous): Humalog®, Apidra® or Novolog® Investigational inhaled insulin: Technosphere® Insulin Inhalation System (Gen2C inhaler) by MannKind Corp. IND 61,729
Study Purpose	
Primary objective of this feasibility study:                      To evaluate the performance of the AP device while the subject is under close medical supervision in the Clinical Research Center (CRC) setting.
 
This objective will be assessed by subjecting the AP device (combined with the Technosphere® Insulin Inhalation Powder) and the subject to several challenging situations, such as meals, exercise, and nocturnal period. The study will evaluate the percent of time the glucose level of the subject remains within pre-specified target ranges:
 
 
• Target range (unless described otherwise): [80-140] mg/dL
 
• Overnight target range: [80-140] mg/dL
 
• Target range 5 hours after meal: [70-180] mg/dL
 
• Target range during exercise: [70-150] mg/dL
 
• Target range 3 hours after exercise: [70-150] mg/dL
 
 
The study will also evaluate the glucose level at 1- and 2-hour postprandial and the area-under-the-curve (AUC) at 6-hour post-prandial.
 
Secondary objectives:                      To evaluate the performance of the AP device combined with the Technosphere® Insulin Powder System:
 
 
• when glucose values are outside of the desirable ranges,
 
• in analyzing the values and duration of the extremes, in particular if <70 mg/dL and <60 mg/dL.
 
• in analyzing adverse events,
 
• in analyzing outside interventions not following the recommendation of the HMS,
 
• if the same subjects were enrolled in this study and the original IDE G110093 study (protocol revision 2.2): comparing the glucose profile between the two clinical studies with and without the Technosphere® Insulin.
 

Study Design	Non-randomized, uncontrolled, feasibility study conducted in the United-States at one clinical site, with one principal investigator.  Overview of the procedures:

	
Following the successful screening and informed consent process:
 
During the week prior to the CRC visit, the subject will review glucose control and insulin pump settings with study staff, with goal to aim for optimal glucose control. (Subject's basal rate settings are used for insulin delivery during closed-loop mode when glucose is predicted to be within determined glucose zones, and insulin to carbohydrate ratios are used in study test meal calculations).
 
Two to three days prior to the CRC visit, the subject will attend an outpatient visit for the insertion, by study staff, of two CGM sensors, as well as to receive training and instructions on how to care for the CGM. The CGM will be in blinded mode during the 2-3 days as an outpatient. The Bayer Contour® NEXT EZ blood glucose meter will be used for all CGM calibrations.
 
Two to three days after this sensor insertion visit, the subject will return to the CRC for approximately 25-28 hours, during which the evaluation of the AP device will occur. The CGM will be unblinded.
 
On the first day of the CRC visit, the subject will arrive at approximately 4:00 pm. If the subject's blood glucose is greater than 250 mg/dL at arrival to the clinic, the study will be rescheduled. All times are +/- 30 minutes.
 

• Closed-loop will start at approximately 4:30 pm.

• A small evening meal (~50g CHO) will be given at approximately 6:30 pm without announcing it to the device, i.e. without providing any information to the device. The meal will be preceded by administering a single dose of Technosphere® Insulin (10U) using the Gen2C inhaler.

• Night time will be from approximately 12:00 am to 7:00 am.

• Another small meal (~50 g CHO) will be given for breakfast at approximately 7:00 am. The meal will be preceded by administering a single dose of Technosphere® Insulin (10U) using the Gen2C inhaler.

• At 11:00 am, the subject will be given a snack (~16 g CHO) and start exercise.

• The subject will exercise for 30 minutes at 50% of his/her target heart rate.

• At approximately 2:00 pm, the subject will be given another snack (~16 g CHO).

• At around 4:30 pm, i.e. 24 hrs after starting, closed-loop will end.

 
During the CRC visit, all diabetes care and use of the AP device will be the responsibility of the investigator. The insulin brand (subcutaneous) used during the CRC session will be the same as the brand used by the subject. Technosphere® Insulin will be delivered using the 10U Gen2C cartridge per the Investigator's Brochure manufacturer's instructions. A detailed plan for diabetes monitoring and for responding to hypoglycemia and hyperglycemia will be in place as described by this protocol. Subject will be monitored closely by trained study staff during the entire CRC visit. A physician will be present at all time.
 
The CGM will be calibrated as required by the manufacturer, as well as approximately 30 minutes before each meal and before bedtime. Additional calibrations may also be performed as required.
 
Blood glucose will be monitored by YSI at least every 30 minutes. More frequent monitoring may be performed as defined in the protocol to ensure the safety of the patient.
 
Each time a YSI measurement will be taken, a finger stick measurement using the CONTOUR® NEXT EZ blood glucose monitoring system will be performed to

--	--

	
collect information, but no decision will be made from the results of the finger stick.
 
If the HMS recommends giving CHO to the subject, the investigator will follow the recommendation. Any other outside intervention by the investigator will terminate the study session for that subject. If clinical results from a subject are found to be suboptimal with excessive hyperglycemia or excessive hypoglycemia alarms, the responsiveness factor of the control algorithm may be adjusted for the study of the next subject.
 
Once the glucose level of the patient is back to more than 90 mg/dL for more than 1 hour, and the glucose level is less than 180 mg/dL with ketones less than 0.6 mmol/L, the patient will be discharged from the CRC.
 
On the day following the CRC visit, the study staff will be in contact, by telephone or in person with the subject for follow-up.

Subject Population	
Adults aged 21-65 years                      Type 1 diabetes mellitus for at least one year                      Using an insulin infusion pump with rapid acting insulin for at least six months

Sample Size	12 to 20 subjects
Duration of the subject participation	Total duration by each subject is expected to be approximately one week from time of contact to review glucose control to follow-up after discharge from CRC visit.
Study Center	Sansum Diabetes Research Institute, Santa Barbara, CA
Inclusion Criteria	
 
• Clinical diagnosis of type 1 diabetes for at least one year and using an insulin pump for at least 6 months with commercially available rapid acting insulin
 
• The diagnosis of type 1 diabetes is based on the investigator’s judgment; C peptide level and antibody determinations are not needed.
 
• Age 21 to 65 years
 
• For females, not currently known to be pregnant or nursing
 
• HbA1c between 5.0% and 10%, as measured with DCA2000 or equivalent device
 
• Forced expiratory volume in 1 second (FEV1) ≥ 70% Third National Health and Nutrition Examination Survey (NHANES III) predicted
 
• Forced vital capacity (FVC) ≥70% NHANES III predicted
 
• Forced expiratory volume in 1 second as a percentage of forced vital capacity (FEV1/FVC) ≥ NHANES III lower limit of normal (LLN)
 
• Willing to perform the calibration of the study CGMs using a finger stick only and willing to follow instructions for insulin pump and CGM wear.
 
• Willing to use the study CGM and study insulin pump during closed-loop.
 
• Able to and agrees to avoid the following medication starting 24 hours before sensor wear through completion of CRC visit: acetaminophen, and
 

	
pseudoephedrine.
 
 
• An understanding of and willingness to follow the protocol and sign the informed consent.
 


Exclusion Criteria
	
 
• Pregnancy (as determined by a positive blood pregnancy test performed in females of childbearing capacity during screening visit and urine test at time of admission for in-patient visit) or nursing mother.
 
• Diabetic ketoacidosis in the past 6 months prior to enrollment requiring emergency room visit or hospitalization
 
• Severe hypoglycemia resulting in seizure or loss of consciousness in the 12 months prior to enrollment
 
• Current treatment for a seizure disorder;           
 
○ Subjects with a history of seizures may be included in the study if they receive written clearance from their neurologist
 
 
 
• Cystic fibrosis
 
• Active infection
 
• A known medical condition that in the judgment of the investigator might interfere with the completion of the protocol such as cognitive deficit.
 
• Mental incapacity, unwillingness or language barriers precluding adequate understanding or co-operation, including subjects not able to read or write.
 
• Coronary artery disease or heart failure.           
 
○ Subjects with a history of coronary artery disease may be included in the study if they receive written clearance from their cardiologist
 
 
 
• Presence of a known adrenal disorder
 
• Active coronary artery disease or heart failure
 
• Active gastroparesis
 
• If on antihypertensive, thyroid, anti-depressant or lipid lowering medication, lack of stability on the medication for the past 2 months prior to enrollment in the study
 
• Uncontrolled thyroid disease           
 
○ Adequately treated thyroid disease and celiac disease do not exclude subjects from enrollment
 
 
 
• Abuse of alcohol
 
• A recent injury to body or limb, muscular disorder, use of any medication, any carcinogenic disease, or other significant medical disorder if that injury, medication or disease in the judgment of the investigator will affect the completion of the exercise protocol
 
• Current use of a beta blocker medication
 

	

• Laboratory results:

○ Hematocrit < 30% or >55%

○ A1C > 10%

○ Abnormal liver or renal function (Transaminase >2 times the upper limit of normal, Creatinine > 1.5 mg/dL)

○ Labs drawn at screening visit or within one month prior to screening (for other purposes) will suffice for enrollment purposes related to hematocrit

• Subject has skin conditions that, in the determination of the investigator, would preclude wearing the study devices (infusion set and sensor), in the abdomen. Examples include but are not limited to: psoriasis, burns, scarring, eczema, tattoos, and significant hypertrophy at sites of device wear; any known allergy to medical adhesives.

• Currently on long-term treatment using prednisone.

• If subject had been on short term treatment of prednisone, defer enrollment until underlying condition and prednisone treatment have resolved.

• Allergy to study drug, food or other study material

• History of asthma, COPD (chronic obstructive pulmonary disease), or any other clinically relevant chronic lung disease

• Respiratory track infection within 4 weeks before screening

• Clinically significant screening ECG, physical examination, laboratory test, or vital sign abnormality

• Exposure to any investigational drug within 30 days.

• History of malignancy within the 5 years before screening (other than basal cell carcinoma)

• Inability, in the opinion of the investigator, to adequately inhale Technosphere® Inhalation powder

• Abnormal spirometry

• Currently smoking or discontinued smoking (including cigarettes, cigars, pipes) over the past 6 months.

• Highly sensitive to insulin: insulin-to-carbohydrate ratio I:C > 1:12.

• Current participation in another investigational trial (unless participation to original protocol of IDE G110093) or has previously participated to this study.

--	--

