changes in glucose concentration. Three levels may be evaluated:  $Q/R$  with a ratio of 1:12, 1:15 and 1:50 (from most responsive to least responsive). The default setting is considered to be the nominal ratio of  $Q/R$  of 1:15. The first subject will be evaluated using that setting. Then, following results from each subject, if results showed poor glucose control, as defined by frequent hypoglycemia alerts or excessive hyperglycemia, in the investigator's opinion, the *responsiveness factor* may be adjusted to the most agile setting of 1:12 or most conservative setting of 1:50 for the next subject.

The total number of subjects will remain 12 to 20 total. Each subject will only be evaluated using one *responsiveness factor* setting. Changes to another setting will be based on prior clinical results and decision of the investigator for the next subject. This will be a clinical decision to add to the overall safety of the study. All changes of the *responsiveness factor* between subjects and their justifications will be documented.

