The glucose level during and after the exercise period has a different profile for each subject because of the difference in the trend preceding the exercise session. There was no hypoglycemic event or HMS alert during the exercise period

In conclusions, this preliminary analysis of the results showed that the AP device is able to detect meals and react appropriately to prevent excessive post-prandial peaks. It also works effectively in anticipating risks of hypoglycemia and alerting the physician / subject to ingest carbohydrate. The redundant safety mechanism functioned as anticipated.

Because of the post-prandial peak, the new clinical study is proposing to use a dose of Technosphere® Insulin Inhalation Powder at the beginning of each meal. TI is a very fast acting insulin. It is anticipated that the TI will mimic the early phase of prandial insulin hence, will reduce the post-prandial peak. This will allow the AP device to operate more effectively as a regulator of glucose level using subcutaneous delivery of insulin. Besides the added TI dose at the beginning of each meal, the clinical design will remain exactly the same (only the meal size of the breakfast will be increased to 50 g of CHO to be the same as the evening meal).

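### The comparison with G110093 cannot be credited to inhaled insulin alone: the CGM is a newer generation in every pair, although the protocol calls the device the same

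*Combined protocol and SAP*

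**What the plan says.** **Sameness.** The Executive Summary presents the trial as a follow-up to an earlier feasibility study and states that "The new proposed study and IDE G110093 use the same device and follow the same clinical protocol", the one stated difference there being the inhaled insulin before meals. The contents entry for section 3.3.4 also calls it the same AP device. The end of section 3.3.4 says that, besides the inhaled dose, "the clinical design will remain exactly the same", with one exception in brackets: breakfast is raised to 50 g CHO.

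**CGM.** The sentence directly after the Executive Summary's sameness statement reads: "The CGM for this proposed study is the next generation of Dexcom CGMs, the G4® System".

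**Pump.** The Executive Summary narrative and section 10.4.1 name only the OneTouch Ping. The device row of the synopsis adds "or the OmniPod® Insulin Management System from Insulet Corp", and sections 1.1 and 1.3 also allow either pump.

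**Controller setting.** Section 1.4 sets a default Q/R of 1:15 and allows 1:12 or 1:50 after poor control. "Changes to another setting will be based on prior clinical results and decision of the investigator for the next subject", and each change must be documented and justified. Section 10.1 also bases the setting on the previous subject's results.

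**The contrast.** The Executive Summary will report 1-hour and 2-hour post-meal glucose and 6-hour AUC "when compared to G110093 to evaluate the impact of the Technosphere® insulin", in subjects who took part in both studies. The synopsis places the comparison of glucose profiles among the secondary objectives, conditional on overlap, and labels it as with versus without inhaled insulin. Section 16 gives no method for it. Section 16.1 bases the end-points on CGM data and treats each patient as his or her own control. Section 16.4.1 makes CGM the default source.

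**The concern.** A subject's own earlier session isolates an added drug only if the rest of the system is alike in both sessions. Here the sensor changed, and the sensor is central to a closed loop: sections 1.2 and 1.4 show that its readings drive both zone-MPC and the HMS. A different sensor can change how much subcutaneous insulin is delivered and when the HMS asks for carbohydrate.

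This is the only with/without comparison of inhaled insulin in the documents. If the newer sensor improves control, the gain would be reported as a drug effect. If the background control is worse in this study, a real drug effect could be hidden. Dinner is the meal whose size was kept, so it looks like the clean comparison, but the sensor change applies there too.

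**Working it through.** The plan gives no alpha, power, SD or effect size for this contrast, so there is no figure to reproduce. The check sets the statements side by side, asks what each remedy can remove, and then illustrates sensitivity.

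**1. What differs between an overlap subject's two sessions, besides the inhaled dose**

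| Element | This study | Status against G110093 | Listed as an exception in section 3.3.4? |
|---|---|---|---|
| CGM | Next-generation G4 (Executive Summary) | Differs, in every pair | No |
| Breakfast size | 50 g CHO | Differs | Yes |
| Pump | Ping or OmniPod (synopsis, 1.1, 1.3) | Possible, not shown | No |
| Q/R | Default 1:15; 1:12 or 1:50 allowed (1.4) | Possible, not shown | No |

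The opening of section 3.3.4 is not in the text available to this review, so G110093's pump and Q/R settings cannot be read. Nothing in the visible text ties an overlap subject's Q/R to the value used in his or her own G110093 session. If the settings did differ, the ratio would be 15/12 = 1.25 from default to most agile, 50/15 = 3.3 from default to most conservative, and 50/12 = 4.2 between the two non-default extremes. The documents do not convert any of these into a glucose effect.

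**2. How the CGM change enters**

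- Control: the sensor drives insulin delivery and HMS warnings.
- Measurement: the sensor supplies the outcome values unless another source is named, and none is named for this contrast.

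Scoring by YSI removes the second route but not the first. Restricting to pairs with the same pump and Q/R removes those two differences if present, but the CGM still differs in every remaining pair.

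**3. Sensitivity illustration**

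Inputs: Table 3-1 (YSI, 12 G110093 subjects). Dinner: 72% in 70-180 and 39% in 70-150 mg/dL. Breakfast: 63% and 45%. Assumption: an even spread of readings across 150-180 mg/dL.

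- Dinner: (72 - 39)/30 = 33/30 = 1.1 percentage points per mg/dL.
- Breakfast: (63 - 45)/30 = 18/30 = 0.6 points per mg/dL.

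| Assumed background shift | Dinner, time in 70-180 | Breakfast, time in 70-180 |
|---|---|---|
| 2 mg/dL | 2.2 points | 1.2 points |
| 5 mg/dL | 5.5 points | 3.0 points |
| 10 mg/dL | 11.0 points | 6.0 points |

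A 5-point change needs 5/1.1 = 4.5 mg/dL at dinner or 5/0.6 = 8.3 mg/dL at breakfast. The shifts are assumed; the documents give none. The calculation fits an upward shift directly. A downward shift also needs a similar density of readings just above 180 mg/dL. Time in range is not the named contrast: for 1-hour and 2-hour glucose, a uniform shift simply carries through one for one.

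**4. Is there a drug-free window?**

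- Closed-loop start to dinner (about 4:30 to 6:30 pm) precedes any inhaled dose. At one YSI reading per 30 minutes it holds about 120/30 + 1 = 5 readings, and it depends on starting glucose and trend, which section 3.3.4 names as sources of variation.
- Midnight to 7:00 am is not drug-free. Section 3.3.4 expects the inhaled dose to change how the device regulates glucose, so the dinner dose can alter later subcutaneous delivery.

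**The case against.** The strongest reply has four parts.

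- **The CGM change is disclosed**, one sentence after the sameness statement. That is true, and a reader who inferred concealment would be wrong. But disclosure does not make the device the same, and section 3.3.4's exception omits the sensor.
- **The pump and Q/R differences are unproven.** This stands. A reader might infer that overlap subjects did change pump or setting. The documents do not show it: G110093's values are not visible, section 1.4 has a default and changes it only after poor control, and several sections name only the Ping. Section 1.3 also says both pumps were validated with the platform.
- **The size is assumed.** This also stands. A reader might take 5 points or 11 points as the estimated bias. They are responses to assumed shifts, on an outcome other than the named contrast.
- **The stakes are low.** The comparison is conditional and secondary, no test or decision rests on it, and section 14 says the goal is not to measure efficacy. That limits the severity, but the plan still states a causal reading that the design does not support.

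It would also go too far to call the contrast worthless. Pairing still removes stable differences between subjects.

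**Conclusion.** The point holds in a limited form. The sameness statements conflict with the protocol's own account of the CGM, and the paired contrast with G110093 cannot be credited to inhaled insulin alone, at either meal. One unlisted difference, the sensor, is certain and present in every pair. Two more, pump and Q/R, are possible but not shown. Breakfast carries the acknowledged meal-size change as well, so dinner is the cleaner meal without being a clean one.

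The size of the confounding is unknown. The figure of 1.1 points per mg/dL at dinner rests on an even spread between 150 and 180 mg/dL and shows only that small background shifts would be visible in time in range. The importance is moderate: this affects what a feasibility study may say about the added drug, not its main time-in-range description.

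**What to change.** 1. Reconcile the Executive Summary and section 3.3.4 so that the CGM generation is listed as an exception alongside breakfast size. State whether pump and Q/R were the same in G110093, if the full section 3.3.4 does not already do so.
2. Describe the contrast, for all pairs, as the combined effect of inhaled insulin and the updated closed loop. Keep that label when pump and Q/R match, because the CGM still differs.
3. Compute 1-hour glucose, 2-hour glucose and 6-hour AUC from YSI, with dinner shown separately from breakfast. Add this to section 16, where Table 16-3 currently lists only a 5-hour post-meal AUC.
4. List CGM model, pump and Q/R for each overlap subject in both sessions. Show same-pump, same-Q/R pairs as a sensitivity analysis.
5. Report the paired YSI difference from closed-loop start to dinner as a descriptive check, noting its few readings and its dependence on starting glucose. Do not treat midnight to 7:00 am as drug-free, and do not use either window as a rule for discarding an effect.

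These are changes of wording and analysis; no dose, controller setting or clinical rule is touched. The cost is retrieving G110093's device records (their availability is assumed, since the documents do not show it), probably few matched pairs, and a more cautious conclusion about inhaled insulin.
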